Diabetic foot ulceration (DFU) is a common and largely preventable complication of diabetes. [1] While most of these ulcers can be treated successfully, some will persist and become infected. Ultimately, nearly one fifth of patients with infected lower-extremity diabetic ulcers will require amputation of the affected limb, resulting in staggering costs for both the patient and the healthcare system. Prevention by identifying people at higher risk is key for better clinical management of such patients. It is not uncommon for patients suffering from diabetes to have concomitant lower extremity edema or venous insufficiency and they subsequently may benefit from graduated compression. However, because of the common association of peripheral arterial disease (PAD) in patients with diabetes, most clinicians are reluctant to apply compressive dressings in fear of exacerbating the symptoms of PAD and possibility of gangrene.

Unfortunately, this area has received comparatively little attention from industry, academia, and insurance providers. A novel low voltage, battery powered medical device, PulseFlow DF® (The Diabetic Boot Company, Ltd. UK) has endeavoured to assist in the treatment of Diabetic Foot Ulcers. The device provides hybrid functionality i.e. mobile air bladder pump at plantar arch and offloading boot. The air bladder inflates to 160mmHg for approx. 1 second then deflates back to atmospheric pressure, allowing the plantar vessels sufficient time to refill. The offloading boot design holds the foot and lower leg in a position that reduces shear and friction forces and provides a reduction in plantar pressure.

The PulseFlow DF is designed to record how many hours of blood pumping it has delivered. This data will be downloaded at each clinic visit. The boot cannot pump blood around your foot unless fitted correctly and the battery is charged up overnight.

Please note that this study is a proof of concept study.

Section D: Purpose and Objectives

The purpose of this study is to conduct an observational study with N=15 diabetic subjects with active foot ulcers to assess whether PulseFlow foot compression device can help improve lower extremity perfusion, whilst improving balance and spatio-temporal parameters of gait.

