Category 2: Research involving greater than minimal risk, but presenting the prospect of direct benefit to the individual subjects.

E2. Subjects

Gender:

Both

Age:

Adult (18-64 yrs), Geriatric (65+ yrs)

Ethnicity:

All Ethnicities

Primary Language:

English, Spanish

Groups to be recruited will include:

Patients

Which if any of the following vulnerable populations will be recruited as subjects?

Vulnerable populations require special protections. How will you obtain informed consent, protect subject confidentiality, and prevent undue coercion?

E3. Pregnant woman/fetus

Will pregnant women and/or fetuses (as described in 45 CFR 46 Subpart B) be enrolled in the research?

No

E4. Neonates

Will neonates of uncertain viability or nonviable neonates (as described in 45 CFR 46 Subpart B) be enrolled in the research?

No

E5. Children

Will children be enrolled in the research?

No

Section F: Design/Procedure

F1. Design

Select one category that most adequately describes your research:

c) Pilot

Discuss the research design including but not limited to such issues as: probability of group assignment, potential for subject to be randomized to placebo group, use of control subjects, etc.

In this proof of concept, intent to treat trial, 15 consecutive patients with diabetes and risk for lower extremity ulcers will be recruited from all study sites. Patients will be consented per the local Institutional Review Board's guidelines and approval for this study.

Inclusion Criteria:

a) Males or females age 18-80 years old with history of type 1 or 2 diabetes and the ability and willingness to provide Informed consent b) Patients with diabetic foot ulcers c) Patient is willing to participate in all procedures and follow up evaluations necessary to complete the study. d) Patients who have undergone lower extremity surgery / amputation may be enrolled into the study to the clinical judgment of the Investigator

Exclusion Criteria:

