Study Day 3, Visit 4 4-week follow-up: All participants will be asked to return to clinic approximately 4 weeks after visit 1. In this visit, outcome assessment using similar assessments described for Study Day 0 will be performed. In addition, perception of benefit and user-friendliness of the PulseFlow DF® will be assessed using a questionnaire. We will take digital photographs.

Participants will be asked to wear a comfortable shirt which holds a small activity monitor (PAMSys) for a period of 48 Hours (2 days). Patients will be requested to return this device via a pre-paid FEDEX envelope

Study Day 4, Visit 5 Follow-up up to three months: Some participants may be contacted by the study coordinator approximately up to three months post the last study visit to document success of wound healing if they continue to use PulseFlow DF after 4 weeks as well as potential incident of re-ulceration, or incident of falls.

We will ask participants to provide an Emergency Contact.

We will ask participants if they would like to be contacted for further studies they may be eligible for.

****Please note that the protocol attached to Section S is from the University of Arizona. The PI initially established this protocol at U of A as it is an investigator initiated study. We have ensured that we have not included any references to U of A in this BCM protocol*****

Section G: Sample Size/Data Analysis

G1. Sample Size

How many subjects (or specimens, or charts) will be used in this study?

Local: 50 Worldwide: 50

Please indicate why you chose the sample size proposed:

We intend to employ a simple minimal risk research protocol to capture data required to realize the goals of this study. The results from this study will help us understand the real clinical needs and optimize the device specifications and form factor to fulfill these needs.

This is an initial proof of concept pilot study. The results of this study will allow for the calculation of an appropriate sample size for a larger proof of superiority (over current standard of care) trial.

G2. Data Analysis

Provide a description of your plan for data analysis. State the types of comparisons you plan (e.g. comparison of means, comparison of proportions, regressions, analysis of variance). Which is the PRIMARY comparison/analysis? How will the analyses proposed relate to the primary purposes of your study?

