PulseFlow DF is an adjunct to standard wound healing therapies for the treatment of diabetic foot ulcer. You must comply with the procedures provided by your doctor or care provider for treating your diabetic foot ulcer.

The study device and technology is completely non-invasive, safe, non-toxic and non-ionizing. The potential risks to you are minimal. However, like any battery powered systems, there is a minimum risk of device malfunctioning. In addition, the study devices are not waterproof, and although they use a low powered battery (similar to a cell-phone battery), in order to avoid any risk or shock the provided devices including activity monitor should not be submerged or saturated with fluids during operations or cleaning.

The assessments described above are expected to be minimal risk and probability and magnitude of harm or discomfort anticipated in the research are not greater in and of themselves than those ordinarily encountered in daily life or during the performance of routine physical or psychological examinations or tests

The duration of this study is 4 weeks and thus the treatment using PulseBoot DF will be terminated at 4 weeks. If subject's foot ulcer has not fully healed at 4 weeks, or is deemed not to be responding, they will be switched to standard of care and a different treatment method as instructed by subject's doctor or care provider. Based on subject's preference and advice of subject's doctor or care provider, participants may continue to use PulseFlow DF for up to 12 weeks.

H2. Data and safety monitoring plan

Do the study activities impart greater than minimal risk to subjects?

Yes

NOTE: The answer to the questions in H2 requires the completion of the form: 'Section H – Data and Safety Monitoring Plan' as an attachment in Section S.

H3. Coordination of information among sites for multi-site research

Is the BCM Principal Investigator acting as the SPONSOR-INVESTIGATOR for this multi-site research?

No or Not Applicable

Is BCM the COORDINATING CENTER for this multi-site research?

No or Not Applicable

Section I: Potential Benefits

Describe potential benefit(s) to be gained by the individual subject as a result of participating in the planned work.

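### Planned enrolment is 15 in Sections D and F1 but 50 in Section G1, and nothing in the available text reconciles the two

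*Combined protocol and SAP*

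**What the plan says.** Three places in the combined protocol and SAP state how many patients are planned.

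- Section D (Purpose and Objectives): the purpose is to "conduct an observational study with N=15 diabetic subjects with active foot ulcers".
- Section F1 (Design): "15 consecutive patients with diabetes and risk for lower extremity ulcers will be recruited from all study sites".
- Section G1 (Sample Size): the form asks "How many subjects (or specimens, or charts) will be used in this study", and the answer is "Local: 50 Worldwide: 50".

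The rationale in G1 contains no calculation. It describes a proof-of-concept pilot and gives its use: "The results of this study will allow for the calculation of an appropriate sample size for a larger proof of superiority".

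On exposure, E1 selects "Category 2: Research involving greater than minimal risk", and H2 answers yes to "Do the study activities impart greater than minimal risk to subjects". H1 states "The duration of this study is 4 weeks" and allows some participants to keep using the device for up to 12 weeks.

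**The concern.** D, F1 and G1 are all current text of one document, and they disagree on a basic design parameter. A site reading D and F1 would close enrolment after the fifteenth patient; a site reading G1 would continue to the fiftieth. The reader cannot tell whether a sixteenth patient is within plan.

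Two things depend on the answer. The first is how many people wear an investigational device in a study that E1 and H2 class as more than minimal risk. The second is how precise the estimates will be when they are used to size the later trial, which is the use G1 names for the results.

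**Working it through.** **Inputs.** 15 (Section D), 15 over all sites (F1), 50 local and 50 worldwide (G1), 4 weeks of treatment (H1). The sections available give no alpha, power, effect size, SD, margin or dropout rate, so neither 15 nor 50 can be reproduced by a sample-size formula. The check is therefore a direct comparison, followed by a test of each reading that might link the figures.

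**Size of the gap.** 50 − 15 = 35 patients; 50 / 15 = 3.33.

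**Could it be site against total?** No. F1's 15 is the total for all sites. G1 gives 50 for the local site and the same 50 worldwide. A local count cannot exceed the all-site count.

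**Could 50 be 15 inflated for dropout?** Required enrolment is n / (1 − d), with n = 15, rounded up:

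| Dropout d | Enrolment needed |
|---|---|
| 10% | 17 |
| 20% | 19 |
| 30% | 22 |
| 50% | 30 |
| 70% | 50 |

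Reaching 50 needs d = 1 − 15/50 = 70%. No available section states any dropout allowance.

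**Could 50 count charts, consents or screenings?** The form question permits charts as a unit. If 50 were such a ceiling, the implied yield is 15/50 = 30%. No available section gives a screening number or a yield, and G1 does not name the unit.

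**Exposure.** If every patient completes the 4 weeks, 15 × 4 = 60 patient-weeks against 50 × 4 = 200. Optional continued use is not counted.

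**Precision of a mean within-subject change.** The half-width in SD units is t(1 − α/2, n − 1) / √n. The documents give no confidence level, so 95% is an assumption and the range is shown:

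| Level | n = 15 | n = 50 | Ratio |
|---|---|---|---|
| 90% | 0.455 | 0.237 | 1.92 |
| 95% | 0.554 | 0.284 | 1.95 |
| 99% | 0.769 | 0.379 | 2.03 |

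**Precision of the SD, which a later sample-size calculation would use.** The 95% limits, as multiples of the observed SD, are √((n − 1)/χ²) at the 97.5% and 2.5% points, assuming normal data and again an assumed level. They are 0.73 to 1.58 at n = 15 and 0.84 to 1.25 at n = 50. Required sample size scales with the SD squared, so the upper limit multiplies it by 1.577² = 2.49 at n = 15 and by 1.246² = 1.55 at n = 50.

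**The case against.** The best defence is that 50 is a ceiling rather than a target. The consent section (J1 and J2) describes chart screening for eligibility. F2 places written consent before screening procedures and removes patients whose vascular assessment shows an ABI below 0.5, so more patients may consent than are treated. This makes unlabelled a real alternative to wrong. It does not rescue G1, which names no unit and is followed directly by a prompt asking why that sample size was chosen.

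A second point is that not everything can be seen. F2 notes that the protocol attached in Section S comes from another institution, where the study began, and H2 calls for a monitoring-plan form that is also attached there. Those attachments are not available, so an explanation there cannot be excluded, and text carried over from the earlier protocol may be how the mismatch arose. The finding is limited accordingly. An explanation elsewhere would still leave D, F1 and G1 giving different numbers without a label.

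Third, the risk argument has another side: G1 itself calls the protocol minimal risk, and H1 describes the risks to participants as minimal. That is a further inconsistency, and it does not alter the uncertainty about how many patients are exposed.

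Fourth, the precision figures are illustrations. The plan sets no precision target, and G2 proposes ANOVA, regression and multivariate tests rather than a single mean change. That is correct, and the contradiction does not rest on them.

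Finally, this is a pilot with no power calculation and no visible stopping rule tied to N, so a lower priority could be argued. The number enrolled is nevertheless a figure the trial relies on, and a 3.3-fold gap is too large to leave open.

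**Conclusion.** The inconsistency stands. Two sections plan 15 patients and one plans 50, and at least one of the three entries is wrong or unlabelled. The documents do not show which number is intended. The difference is 35 patients. With full 4-week use it is 140 patient-weeks of device exposure (200 − 60), and it changes the precision of a mean change about two-fold at any usual confidence level. The contradiction needs no assumption. The exposure figure assumes complete use, and the precision figures assume a confidence level, a simple mean change and, for the SD limits, normal data. The conclusion covers only the text available, which excludes the Section S attachments. The point must be fixed.

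**What to change.** The sponsor should confirm the intended enrolment and state the same target in Section D, F1 and G1. If 50 is a ceiling on charts, consents or screenings, G1 should say so and give the enrolment target beside it. As an option, G1 could add the precision that the confirmed number gives, for example the half-width of the confidence interval for a mean change.

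The cost is wording in up to three places, plus a check that the consent form and the Section S attachments carry the same number. The correction does not itself change procedures or analyses. It does have consequences either way. If 50 is confirmed, D and F1 will describe 35 more patients than they do now. If 15 is confirmed, the G1 entry falls or needs a label, and the regression in G2 should be read against it: four predictors entered as single linear terms leave 15 − 5 = 10 residual degrees of freedom, against 50 − 5 = 45.

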Primary Endpoints: 1. Lower Extremity Perfusion: Measurement of lower extremity perfusion at 4 weeks of continuous device usage. Peripheral perfusion will be measured at baseline, 48 hours, 1 week and 4 weeks. Ankle Brachial Index (ABI) and Skin Perfusion Pressure (SPP) will be used to evaluate perfusion status for all study participants.

2. Plantar Pressure: Measurement of plantar pressure compared to the standard (non-PulseFlow DF) offloading boot.

Secondary Endpoints:

The following secondary effectiveness endpoints will be evaluated but success will not be required for determining success of the study. 1) Balance: Improvement in balance and decrease in fall risk as measured using a validated body worn sensor system at baseline and 4 weeks. 2) Activity Measurement: Activity measurement during 48 hours of continuous daily physical activity using a validated body worn sensor system, measured at baseline and 4 weeks. 3) Gait assessment using validated wearable technology at baseline and 4 weeks.

Primary Safety Endpoints: 1) The occurrence of adverse events during the four (4) weeks of the study treatment that are possibly related, probably related, or definitely related to PulseFlow DF (e.g. deterioration in wound condition such significant increase in wound size, infection, etc, falls, serious adverse events) will be properly reported.

Other assessments: 1) Usability assessment 2) Patient perception of benefit and level of comfort (Scoring System); 3) Adherence to use of offloading boot; and 4) Others: Quality of life, fear of falling, frailty, etc.

The key goals of the proposed project are to test whether a specially designed compression device can improve lower extremity perfusion, whilst also simultaneously improving the balance and walking performance. We envision the use of this specially designed offloading device with compression capability will help reduce the incidence of diabetic foot ulcers in high-risk diabetic patients. In addition, we assumed the proposed device might enhance daily physical activity as well as walking performance. We will conduct a prospective clinical study to validate these hypotheses. Potential changes in walking and spontaneous daily physical activities will be assessed using validated technologies that include walking analyzer system, balance assessment using body worn sensors, and computerized pressure insoles.

Section E: Protocol Risks/Subjects

E1. Risk Category

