Physical Performance Tests - Gait assessment: Gait performance will be assessed using by a validated body worn sensors (LegSys™, Biosensics LLC, USA). The device uses five sensor modules respectively attached to right and left anterior shins, right and left anterior thighs, and posteriorly to the lower back. Based on the subject’s height and using a two-link inverse pendulum model the following spatio-temporal gait parameters will be estimated: velocity, stride length, stride time, double support, single support, stride-to-stride variability, and gait initiation [20]. In addition, the COM range of motion during walking will be calculated by using the data from the sensor attached to lower-back. Gait will be assessed over a distance of 20 meters while wearing PulseFlow DF® under 2 conditions: (1) walking at habitual speed (2) walking at maximum speed (fast walking). In addition, the above tests will be repeated while wearing removable cast walker (RCW), which is a standard offloading device.

Plantar Pressure Assessment: The efficacy of PulseFlow DF® to reduce plantar pressure will be examined using computerized pressure insoles® (Fscan®, TekScan, Boston, MA). Subjects will be ask to walk a distance of approximately 20 feet at habitual speed while wearing a standard offloading boot and then while wearing PulseFlow DF®. In addition, to ensure that PulseFlow DF® is providing a comparable offloading to a standard offloading device, plantar pressure during standing (approximately 30 seconds) will be assessed while wearing a standard offloading device (e.g. Aircast Walker) and results will be compared while wearing PulseFlow DF®.

Objective assessment of physical activity: Spontaneous daily physical activities as well as the risk of falling during activity of daily living are quantified using a validated body worn sensor named PAMSys™ (Biosensics, LLC, USA). PAMSys is a small long-term recording movement sensor which is unobtrusively inserted into a comfortable shirt (PAMshirt™). The system contains inertial sensors with software developed to identify postural positions and movements such as walking, standing, sitting, or lying during a measuring period of 48 hr. It has proven to be sensitive (87–99%) and specific (87–99.7%)[21, 22] for postural position and detection of walking in different samples of older adults and patient groups.

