This study includes three hypotheses. To examine whether the proposed PulseFlow DF will provide comparable offloading as compared to removable cast walkers measured through a repeated measures study design for in shoe pressures (H1), we will use ANOVA and Fisher's exact tests for intra-subject reduction of peak pressures, pressure time integrals and Dynamic Plantar Loading Index.

To examine whether the proposed PulseFlow DF will help improve macro and micro-circulation in the lower extremity of patients (H2), we will use the similar analytical plan explained above by considering change in Skin perfusion pressure and ABI as dependent variables. For identifying the predictors, we will use multiple linear regression model and Anova (n-way). The independent variables will be severity of neuropathy quantified using Semmes Weinstein Monofilament, the level of activity, BMI, and age.

To examine whether the proposed PulseFlow DF will improve the activity level and quality of life (H3), we will use ANOVA multivariate test. The dependent variables will be number of total steps per day, duration of walking and standing, duration of longest episode of walking (i.e. continuous walking without stop), number of walking episode, duration of sit-to-stand and stand-to-sit postural transition, and SF12. We will use multiple linear regression model and multi-variant test to examine the effect of confounding parameters such as weather condition, BMI, age, etc.

Section H: Potential Risks/Discomforts

H1. Potential Risks/Discomforts

Describe and assess any potential risks/discomforts; (physical, psychological, social, legal, or other) and assess the likelihood and seriousness of such risks:

Some of potential risks could be discomfort, insufficient offloading, and uncomfortable level of compression to your plantar arch. It is important to notify us if you feel discomfort on wearing PulseFlow DF or if you feel excessive pressure to your feet because of wearing the PulseFlow DF.

You should always inspect the wound at each dressing change and comply with instructions providing by your doctor or wound care provider. You should immediately notify us or contact clinic, your doctor, or care provider if you feel the condition of your wound has been deteriorated. The signs of wound deterioration will be discussed with you by your doctor or care provider who treats your wound.

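### H1 asks whether offloading is comparable, but the tests named in G2 look for a difference and cannot answer that when the boots are similar; Fisher's exact test also does not fit the paired, continuous pressure measures

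*Combined protocol and SAP*

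**What the plan says.** - **The question.** G2 states H1 as whether PulseFlow DF "will provide comparable offloading as compared to removable cast walkers", "measured through a repeated measures study design for in shoe pressures".
- **The analysis.** The same sentence of G2 names ANOVA and Fisher's "exact tests for intra-subject reduction of peak pressures, pressure time integrals and Dynamic Plantar Loading Index".
- **Status.** The second primary endpoint in Section D is "Measurement of plantar pressure compared to the standard" offloading boot.
- **Data collection.** Under Plantar Pressure Assessment in F2, each subject walks "while wearing a standard offloading boot and then while wearing PulseFlow DF", so the data are paired. F2 introduces the insole assessment as one of the device's efficacy "to reduce plantar pressure will be examined using computerized pressure insoles". It attaches the comparability aim to a second test, made to ensure that the device "is providing a comparable offloading to a standard offloading device, plantar pressure during standing" being compared between boots.
- **Visits.** For the 4-week visit, F2 calls for assessments similar to those at Study Day 0, so the boots may be compared twice.
- **Purpose and size.** G1 says "This is an initial proof of concept pilot study", whose results will be used to size a later superiority trial. Section D and F1 give 15 subjects; G1 gives 50.
- **Not found in the text supplied.** There is no margin, interval criterion, significance level, SD of the paired difference, or cut-off that would make the pressure measures categorical.

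**The concern.** The aim and the tests point in different directions. A difference test can reject equality; failing to reject it does not establish similarity. If PulseFlow DF offloads about as well as the cast walker, the expected output is a set of non-significant p-values. G2 does not say what H1 then concludes, for a primary endpoint.

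Fisher's exact test is a separate problem. It compares counts in independent groups, whereas the three listed measures are continuous and come from the same people in both boots.

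At stake is whether the pilot can say anything usable about offloading. G2 asks for p-values where an estimate of the paired difference, with its uncertainty, would both answer the question and inform the next trial. Insufficient offloading is itself listed as a potential risk in H1 of Section H.

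A smaller gap is that G2 does not say whether its hypothesis concerns walking or standing, or which visit.

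**Working it through.** The plan gives no power, margin or SD for this comparison, so there is no figure of its own to reproduce. What follows is illustration.

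**Inputs.** n = 15 (Section D, F1) and n = 50 (G1). Assumed: a two-sided 5% paired test, normally distributed differences, one paired difference per subject, and effects *d* in SDs of that difference.

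**1. Boots truly equal (d = 0).** Each measure is non-significant with probability 1 − 0.05 = 0.95, at any n. For three independent measures, the chance that all are non-significant is 0.95³ = 0.857. With equal positive correlation, simulation gives about 0.87 at correlation 0.5 and 0.90 at 0.8, at either n. Hence 86-90%.

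**2. PulseFlow DF truly worse by d.** P(non-significant) = P(|T| < t₀.₉₇₅,ₙ₋₁), where T is noncentral t with n − 1 degrees of freedom and noncentrality d√n. The critical values are 2.145 (n = 15) and 2.010 (n = 50). At d = 0.5 the noncentrality is 0.5√15 = 1.94 and 0.5√50 = 3.54.

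| True deficit (SD) | n = 15 | n = 50 |
|---|---|---|
| 0.3 | 81% | 45% |
| 0.5 | 56% | 7% |
| 0.8 | 18% | <1% |
| 1.0 | 5% | <1% |

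**3. What an interval would show.** The 95% CI half-width is t₀.₉₇₅,ₙ₋₁/√n: 2.145/√15 = 0.554 SD and 2.010/√50 = 0.284 SD. An observed deficit that just misses significance sits one half-width from zero, so its interval reaches twice that far: 1.11 SD worse at n = 15 and 0.57 SD worse at n = 50. The p-value alone hides this.

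**4. Fisher's exact test.** It needs categories, and none are defined. Suppose each measure were split at its median and the paired results entered as if independent. The simulated type I error (nominal 0.05, 4,000 trials per setting) is then:

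| Within-subject correlation | n = 15 | n = 50 |
|---|---|---|
| 0 | 0.015 | 0.032 |
| 0.5 | 0.005 | 0.009 |
| 0.8 | 0.0005 | 0.0008 |

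The stronger the pairing, the less often the test rejects, so a real difference becomes easier to miss.

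**5. If a comparability claim were wanted.** With a true difference of zero and one-sided 2.5%, the margin that gives 80% power by noncentral t is about 0.78 SD at n = 15 and 0.40 SD at n = 50.

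**The case against.** - **The plan never says that non-significance will be read as comparable.** This is correct. A reader might infer that the study would declare comparability from a large p-value, but no such rule is written. The endpoint in Section D is phrased as a measurement, and no success criterion is attached to H1. What stands is narrower: the named tests cannot support the stated aim.
- **The aim may be superiority.** Both G2 and F2 speak of reducing pressure. On that reading a difference test fits, and a significant reduction would also show offloading at least as good. But H1's own word is comparable, F2 repeats it, and the similar-boots case still has no criterion.
- **ANOVA suits paired data.** This is accepted. G2 recognises the repeated-measures design, and a repeated-measures ANOVA of two boots readily yields the paired difference and its interval. A reader might infer that the whole H1 analysis ignores the pairing; the text does not support that. The objection does not rescue Fisher's test.
- **It is a pilot.** Also accepted. No margin need be imposed and estimation is enough, but G2 does not ask for the estimate.
- **The sizes are assumed.** True. Without an SD or a clinically relevant deficit, nobody can say whether 0.5 SD matters for offloading.
- **A fuller plan may sit in the protocol attached in Section S.** That attachment was not available, so the statement about a missing margin is limited to the text supplied.

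**Conclusion.** Wrong as written, and worth fixing because it concerns a primary endpoint. H1 asks about similarity, G2 names tests of difference, and when the boots are similar the plan cannot turn the expected result into an answer. That result is 95% non-significance per measure, or about 86-90% for all three together, assuming equal correlations of 0 to 0.8. Fisher's exact test should not be used on these data as described. ANOVA may stay if it is run as repeated measures.

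The size of the risk depends on the sample size, which the documents give inconsistently. With 15 subjects, non-significance remains common for true deficits up to about 0.8 SD; with 50, only for deficits below about 0.5 SD. These figures assume a two-sided 5% test of one measure and measure no actual harm. The mismatch and the Fisher's point do not depend on them.

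**What to change.** In G2, replace the H1 tests with wording such as:

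> For each pressure measure we will report the within-subject difference or ratio, PulseFlow DF versus removable cast walker, with its paired (repeated-measures) 95% CI, separately for walking and standing and for each visit at which both boots are tested. The baseline visit is the main comparison unless another visit is named before data are seen. A non-significant difference will not be read as comparable offloading.

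Delete Fisher's exact test. Use McNemar's test only if a paired binary outcome with a stated cut-off is defined. Because G2 refers H2 back to the H1 analysis, check that H2 does not inherit the deleted test.

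Only if a comparability claim is wanted: before data are seen, fix one measure, one condition, one visit and a justified margin, and require the worse-side CI limit to lie within that margin. Otherwise report the interval and make no claim.

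**Cost.** Wording in G2 only; no new data. The price is a weaker conclusion, with a 95% CI half-width of about 0.55 SD at n = 15 or 0.28 SD at n = 50.
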